6.5.3 Clinical Evaluation of MRI Scan

The radiologist will review the clinically-indicated MRI scan for diagnostic interpretation. The following information will be collected regarding the MRI scan, and are not limited to:

- Primary reason for MRI scan
- Body region scanned (non-thoracic) (e.g. brain, cervical spine, lumbar spine, knee, shoulder, hip, hand/wrist)
- MRI System used (i.e. brand, model, software version, etc.)
- Duration of scan (min)
- Whole body SAR
- Image quality (i.e. sufficient or insufficient to interpret the MRI image)
- Clinical Diagnosis (e.g. joint abnormality, vascular abnormality, no abnormalities, etc.)

6.5.4 Data Submission

Once all the required testing has been performed at this visit, complete and submit the Enrollment and MRI Scan Case Report Forms to St. Jude Medical. If an adverse event or death occurred, submit an Adverse Event, Death Case Report Form, and Product Out of Service Case Report Form, as applicable. Report any deviations or withdrawals by submitting a Deviation or Withdrawal Case Report Form.

Export the MRI scan onto a CD, or other form of electronic media in DICOM format, and send to St. Jude Medical. Upload pre and post MRI scan device session records through the EDC study portal or Merlin.net. It is recommended that the following device printouts and measurements be maintained at the site.

- FastPath Summary
- Test Results with Freezes, Include Battery & Leads
- Wrap-up Overview with full parameters
- Upload device session record

6.6 Follow-Up Visit Procedures

The subject's scheduled follow-up visits will be based upon the change in the device parameters from the MRI Scan Visit (pre-MRI scan to post-MRI scan measurements).

Clinical Investigational Plan

If the subject had a follow-up visit at another institution, then the follow-up data, including device measurements and pertinent medical records may be obtained per the medical record release authorization statement in the informed consent.

6.6.1 Significant Parameter Changes:

Table 7. List of Significant Parameter Changes Requiring Multiple Follow-Ups

A change in remaining battery capacity of $\geq 2\%$
A change in pacing lead impedance > 50 ohms
A change in high-voltage lead impedance (HVLI) ≥ 7 ohms
Decrease in P wave sense amplitude $\geq 50\%$
Decrease in R wave sense amplitude $\geq 25\%$
Increase in capture threshold $\geq 0.5V$ at the pre-programmed pulse width

6.6.2 Subjects with significant parameter changes requiring multiple follow-up visits

Subjects with any of the significant parameters changes shown in Table 7 above will require multiple follow-up visits to ensure patient safety and appropriate device function. A total of 2 follow-up visits will be scheduled:

- 1) Within 2 to 12 days after the MRI scan
- 2) 1 Month (-7/+ 14 days) after the MRI scan

6.6.3 Subjects requiring only a single follow-up visit

Subjects that did not have any of the significant parameters changes shown in Table 7 will be required to return for a single follow-up visit at 1 month (-7/+14 days) after the MRI scan.

6.6.4 Unscheduled visits

An unscheduled visit is defined as a visit that occurs after the MRI Scan Visit where the subject is seen in clinic due to an ADE, SADE, or UADE.

6.6.5 Device Assessment during Follow-Ups

For any scheduled or unscheduled follow-up visit:

- 1) Determine the subject's underlying rhythm
 - If there is no intrinsic rhythm when the device is programmed to pace at 40 bpm, the subject is considered pacemaker dependent.
- 2) Obtain the following measurements for all leads, as applicable, with the permanently programmed parameters.
 - Remaining battery capacity
 - Capture threshold for all leads

Clinical Investigational Plan

- Sensing amplitude for RA and RV leads
- Pacing lead impedance for all leads
- HVLI impedance

NOTE: *RV capture thresholds are not required to be obtained if a high ventricular rate is present (e.g. 110bpm). If available, sites should use the automatically obtained pacing capture threshold from the most recent archival data as a substitute for the in-clinic capture threshold. RV sensing measurements are not required if the subject's intrinsic rate has been established to be ≤ 40 beats per minute.*

- 3) Evaluate the subject for adverse events (ADEs, SADEs, UADEs).

6.6.6 Data Submission

Once all the required assessments have been performed at the follow-up visit, complete and submit the Follow-Up Case Report Form to St. Jude Medical. If an adverse event, revision procedure, or death occurred, submit an Adverse Event, Death, System Revision, and/or Product Out of Service Case Report Forms, as applicable. Report any deviations or withdrawals by submitting a Deviation or Withdrawal Case Report Form.

6.7 System Revisions

A System Revision CRF should be completed for all types of revisions such as pulse generator replacement, lead replacement and lead repositioning. The subject's follow up schedule is not affected in any way.

If the subject has the SJM pacemaker, ICD, or CRT device removed at any time during the study, and the subject will not receive a replacement SJM device, follow the subject for 30 days, and withdraw the subject from the study. Complete a System Revision CRF and Product Out of Service CRF, withdrawal CRF and submit through EDC.

In cases where only the device pocket is revised (leads are not repositioned, leads have not been disconnected from the device), a System Revision CRF is not required to be submitted.

6.8 Subject study completion

The subject's participation in this study is complete after the last scheduled follow-up per sections 6.6.2 or 6.6.3, as applicable. When the subject's participation in the clinical study has been completed the subject will return to standard medical care as per physician's recommendation.

Clinical Investigational Plan

6.9 Criteria and Procedures for Subject Withdrawal or Screen Failure

Subjects must be informed about their right to withdraw from the study at any time and for any reason without sanction, penalty or loss of benefits to which the subject is otherwise entitled and withdrawal from the study will not jeopardize their future medical care or relationship with the investigator. Subjects will be asked to specify the reason for the termination, but have the right not to answer.

The investigator may decide to withdraw a subject from the study at any time with reasonable rationale. The subject's future care will not be influenced by a decision, voluntary or otherwise, to withdraw from the study. All reasonable efforts should be made to retain the subject in the clinical study until completion of the study.

Reasons for subject's withdrawal include, but are not limited to:

- Subject refuses to continue participating in the study
- Subject is deceased (cause must be documented)
- Subject's non-compliance
- Subject's participation is terminated by the PI or investigator, although the subject consented, since participation is no longer medically appropriate
- Subject receives a non-SJM replacement device during a system revision (subject will be followed for 30 days)
- Subject is 'lost to follow up': Subject does not adhere to the scheduled follow up visits but has not explicitly requested to be withdrawn from the clinical study. (This does not apply to missed visits). Site personnel should at all times make all reasonable efforts to locate and communicate with the subject in order to achieve subject compliance to the scheduled follow up visits:
 - 1) A subject will be considered 'Lost to Follow Up' after a minimum of 2 phone calls of a physician or delegate at the investigational site to the subject or contact. These 2 phone calls need to be documented in the subject's hospital records.
 - 2) If these attempts are unsuccessful, a certified letter should be sent to the subject's last known address or general practitioner (GP) and a copy of this letter should be maintained in the subject's hospital records.

If a subject withdraws from the clinical study, the site will record the subject's reasons for withdrawal, on a Withdrawal CRF.

When subject withdrawal from the clinical study is due to an adverse event the subject will be followed until resolution of that adverse event or determination that the subject's condition is stable. The status of the subject's condition should be documented at the time of withdrawal.

Clinical Investigational Plan

Screening Failure: A subject may also become a screen failure based if the subject's participation ended prior to enrollment in the study. Refer to section 6.3.1.1. Complete a Withdrawal CRF for screen failure subjects and note that the subject is a screen failure.

6.10 Description of Activities performed by Sponsor Representatives

Trained sponsor personnel may perform certain activities to ensure compliance to the clinical investigational plan and may provide technical expertise. Sponsor representatives may perform the following activities:

- Verifying MRI scan parameters on the programmer at the MRI Scan Visit.
- Programming of the device per protocol, and/or as directed by the investigator/designee.
- Interrogation of and testing the device at any study visit (scheduled or unscheduled): remaining battery capacity, capture, sense, pacing and HVLI measurements

While sponsor representatives may perform these activities, the principal investigator remains responsible for ensuring all study data is collected as required per protocol. Deviations resulting from failure to comply with protocol requirements will be reported through completion of a Deviation CRF.

7.0 Compliance to the CIP

7.1 Adherence to the Clinical Investigation Plan (Protocol Deviations)

A deviation is defined as an event where the clinical investigator, site personnel, sponsor or sponsor representative did not conduct the clinical study according to the Clinical Investigational Plan, IRB requirements or the Investigator Agreement. The investigator is not allowed to deviate from the CIP, except as specified under emergency circumstances.

In some cases, failure to comply with the CIP may be considered failure to protect the rights, safety and well-being of subjects, since the non-compliance exposes subjects to unreasonable risks. For example, failure to adhere to the inclusion/exclusion criteria: these criteria are specifically defined by the Sponsor to exclude subjects for whom the device is not beneficial and the use involves unreasonable risks. This may be considered failure to protect the rights, safety and well-being of the enrolled subject. Similarly, failure to perform safety assessments intended to detect adverse events may be considered failure to protect the rights, safety and well-being of the enrolled subject. Investigators should seek minimization of such risks by adhering to the CIP.

Simultaneously, in the event that adhering to the CIP exposes the subject to unreasonable risks, the investigator is also required to protect the rights, safety and well-being of the subject by intentionally deviating from the requirements of the CIP, so that subjects are not exposed to unreasonable risks.

Clinical Investigational Plan

It is the responsibility of the investigator to provide adequate medical care to a subject enrolled in a study.

Regulations require that the PI maintain accurate, complete, and current records, including documents showing the date of and reason for every deviation from the Clinical Investigational Plan. Relevant information for each deviation will be documented on a Deviation Case Report Form. The site will submit the CRF to St. Jude Medical.

Regulations require Investigators obtain approval from St. Jude Medical and the IRB [as required] before initiating changes in or deviations from the protocol, except when necessary to protect the life or physical well-being of a subject in an emergency. Under emergency circumstances, deviations from the CIP to protect the rights, safety and well-being of human subjects may proceed without prior approval of the sponsor and the EC. Such deviations shall be documented and reported to the sponsor and the EC as soon as possible, but no later than 5 working days.

Prior approval must be requested when the PI anticipates, contemplates, or makes a conscious decision to depart from the CIP, except when unforeseen circumstances are beyond the investigator's control (e.g. a subject who fails to attend a scheduled follow-up visit, a subject is too ill to perform a CIP-required test, etc.). All deviations, including those beyond the investigator's control, must be reported on a CRF.

To obtain approval, the Principal Investigator may call or email and discuss the potential deviation with St. Jude Medical or designee prior to initiating any changes.

All deviations must be reported to appropriate regulatory authorities in specified timelines (if appropriate).

Investigator will notify St. Jude Medical and the reviewing IRB within 5 working days of:

- Any deviation to protect the life or physical well-being of a subject in an emergency
- Any failure to obtain informed consent

Investigators or the designee must notify St. Jude Medical, Inc. as soon as possible and complete the Deviation CRF. The Investigator is required to adhere to local regulatory requirements for reporting deviations to IRB.

7.2 Repeated and Serious Non-compliance

In the event of repeated non-compliance or a one-time serious non-compliance, as determined by the Sponsor, a Clinical Research Associate or clinical representative will attempt to secure compliance by one or more of the following actions:

Clinical Investigational Plan

- Visiting the investigator
- Contacting the investigator by telephone
- Contacting the investigator in writing
- Retraining of the investigator

If an investigator is found to be repeatedly non-compliant with the signed agreement, the CIP or any other conditions of the clinical study, the Sponsor will either secure compliance or, at its sole discretion, terminate the investigator's participation in the clinical study.

8.0 Adverse Device Effect

8.1 Definitions

8.1.1 Medical Device

Any instrument, apparatus, implement, machine, appliance, implant, software, material or other similar or related article

(a) Intended by the manufacturer to be used, alone or in combination, for human beings for one or more of the specific purpose(s) of

- Diagnosis, prevention, monitoring, treatments or alleviation of disease,
- Diagnosis, monitoring, treatment, alleviation of, or compensation for, an injury,
- Investigation, replacement, modification, or support of the anatomy or of a physiological process,
- Supporting or sustaining life,
- Control of conception,
- Disinfection of medical devices and

(b) Which does not achieve its primary intended action in or on the human body by pharmacological, immunological or metabolic means, but which may be assisted in its intended function by such means.

8.1.2 Adverse Device Effect (ADE)

An adverse device effect is an adverse event related to the use of an investigational medical device.

This definition includes adverse events resulting from insufficient or inadequate instructions for use, deployment, implantation, installation, or operation, or any malfunction of the investigational medical device.

This definition includes any event resulting from the use, error, or from intentional misuse of the investigational medical device.

Clinical Investigational Plan

8.1.3 Serious Adverse Device Effect (SADE)

Adverse device effect that has resulted in any of the consequences characteristic of a serious adverse event:

- Death
- A serious deterioration in the health of the subject, that either resulted in:
 - A life-threatening illness or injury OR
 - A permanent impairment to a body structure or a body function OR
 - An in-patient or prolonged hospitalization OR
 - A medical or surgical intervention to prevent life-threatening illness or injury or permanent impairment to a body structure or a body
 - Fetal distress, fetal death or a congenital abnormality or birth defect

A planned hospitalization for a pre-existing condition, or a procedure required by the CIP is not considered a serious adverse event.

8.1.4 Unanticipated Adverse Device Effect (UADE)

As defined in 21 CFR §812.3, unanticipated adverse device effects (UADE) are defined as any serious adverse effect on health or safety or any life-threatening problem or death caused by, or associated with, a device, if that effect, problem, or death was not previously identified in nature, severity, or degree of incidence in the clinical investigational plan or application (including a supplementary plan or application), or any other unanticipated serious problem associated with a device that relates to the rights, safety, or welfare of subjects.

If an unanticipated adverse device effect occurs, the investigator must notify St. Jude Medical and the IRB/MEC immediately, but no later than 10 working days of the investigator's knowledge of the event, as required by 21 CFR §812.150. St. Jude Medical will take any steps necessary to investigate the event, and will be responsible for notifying FDA and all other participating IRBs/MECs and investigators.

8.2 Reporting of MRI Scan-Related Adverse Device Effects

An ADE or SADE related to the following should be reported as soon as possible, but no later than 10 working days, to St. Jude Medical: clotting, pulmonary embolism, or heating of the device pocket during the MRI scan. These events are likely to be associated with symptoms occurring during or immediately following the MRI scan and may manifest as chest pain, shortness of breath, or changes in vital signs during or immediately following the MRI scan. To ensure all ADEs or SADEs related to or caused by the MRI scan are appropriately captured, follow the instructions in section 6.5.2 above.

Clinical Investigational Plan

8.2.1 Complication

A complication is defined as an SADE that requires an invasive intervention or leads to death.

8.2.2 MRI scan related complication

A complication is deemed to be MRI related if it is caused by or related to the interaction between the leads, SJM device (pacemaker, ICD, or CRT) and the MRI system that occurs during the MRI scan and includes the time the subject is within the 5 Gauss line of the MRI system or up through the completion of the MRI Scan visit. The MRI scan related complications will be based on the CEC adjudication data.

8.3 Procedure for assessing, recording and reporting ADEs, SADEs, and UADEs:

Safety surveillance within this study and the safety reporting, both performed by the investigator, starts as soon as the subject is enrolled in the study. Enrollment occurs after the subject signs the main study consent, meets all of the inclusion and none of the exclusion criteria, and the subject's device has been programmed for the MRI environment. The safety surveillance and the safety reporting will continue until the completion of the Post MRI follow-up visit(s), the subject is deceased, the subject/investigator concludes his participation into the study or the subject/investigator withdraws the subject from the study, except as otherwise specified in the CIP.

Once the subject's device has been programmed for the MRI environment, according to the protocol, all adverse device effects (whether serious or not-serious) and potential UADEs will be collected and reported to the Sponsor on an Adverse Event case report form through the EDC system.

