8.3.2 Criteria and guidelines for reportable events

Records relating to the subject's subsequent medical course must be maintained and submitted (as applicable) to the Sponsor until the event has subsided or, in case of permanent impairment, until the event stabilizes and the overall clinical outcome has been ascertained. Adverse events will be monitored until they are adequately resolved. The status of the subject's condition should be documented at each visit.

The investigator will report the event to the IRB per their reporting requirements.

Clinical Investigational Plan

Reportable events to sponsor are considered:

- ADEs, SADEs, and UADEs caused by or associated with the MRI scan (except unavoidable events related to the MRI scan)
- Unavoidable ADEs whose conditions worsen or continue beyond the time frame listed in the Unavoidable events tables.
- All ADEs and SADEs that are not associated with the MRI scan

All above events will be reported to the Sponsor, as soon as possible, but no later than 10 days of first learning of the event. A list of foreseeable adverse events and anticipated adverse device effects include, but are not limited to, those listed in Table 1. Refer to section 3.3 for full details.

The Sponsor will ensure that all adverse events are reported to the relevant authorities as per regulations. The description of the adverse event, date of the adverse event, treatment and resolution of the reportable adverse events will be reported, as applicable, to the relevant authorities per regulations. Additional information may be requested, when required, by the Sponsor in order to support the reporting of AE CRFs to regulatory authorities.

The investigator must notify the IRB, if appropriate, in accordance with national and local laws and regulations, of the AE CRFs reported to the Sponsor.

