14.0 Study Committees

14.1 Clinical Events Committee (CEC)

The CEC is responsible for providing an independent review and adjudication of CIP pre-defined clinical events. The CEC will consist of at least 3 members. The CEC will be comprised of independent and unblinded physicians that are not investigators or steering committee members in the trial. St. Jude Medical will appoint members of the CEC and the

Clinical Investigational Plan

chairperson. St. Jude Medical may facilitate the CEC meeting, but will not be voting members.

Reportable events to be collected under this protocol will be adverse device effects outlined in section 8. The CEC will base their final adjudication on the information provided on the case report forms, medical records, and their clinical knowledge and experience. The CEC will also review and classify all subject deaths under this protocol. The primary function, responsibilities and membership of the CEC will be described in detail in a CEC charter.

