14.2 Steering Committee (SC)

The Steering Committee advises the sponsor during a clinical study, such as in the development of the study CIP, during the conduct of the study, during data analysis and/or presentation/publication of the study results. For this study, the Steering Committee will also monitor the overall safety through ongoing monitoring of adverse event and death rates. The primary function, responsibilities and membership of the SC will be described in detail in a Steering Committee charter.

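### Apart from deaths and a few objective triggers, a non-fatal event reaches the independent CEC only after the site judges it device-related, so the CEC cannot recover a serious event the site called unrelated

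*Combined protocol and SAP*

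**What the plan says.** Reporting lies with the site. Section 8.3 states: "Safety surveillance within this study and the safety reporting, both performed by the investigator, starts as soon as the subject is enrolled". From MRI programming onward, what is sent in is "all adverse device effects (whether serious or not-serious) and potential UADEs will be collected and reported to the Sponsor".

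Section 8.1.2 builds relatedness into the term: "An adverse device effect is an adverse event related to the use of an investigational medical device". Every line of the reportable list in section 8.3.2 is an ADE, SADE or UADE. One line covers device effects the site does not link to the scan: "All ADEs and SADEs that are not associated with the MRI scan".

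Section 14.1 sets the CEC's remit for non-fatal events: "Reportable events to be collected under this protocol will be adverse device effects outlined in section 8". Deaths are treated differently: "The CEC will also review and classify all subject deaths under this protocol".

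Under section 8.2.1 a complication is a subset of SADEs: those that are fatal or need an invasive procedure. Section 8.2.2 takes the MRI-related complication count from CEC adjudication. Sections 4.4.2 and 12.1.3 list that count among the additional data.

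**The concern.** Independent adjudication is there to take the relatedness decision away from an unblinded site. Here the site's decision comes first and determines which events are adjudicated. If the site wrongly calls a serious non-fatal event unrelated to the device, no form is required and the CEC has nothing to review. The protocol avoids this for deaths, which are all reviewed, but not for other serious events.

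Table 1 lists thrombus formation, embolism, pulmonary embolism and induced VT/VF as potential MRI-related events. Surveillance runs for about a month after the scan. A site could plausibly attribute a delayed presentation of one of these to the patient's underlying disease. At stake is the descriptive safety summary: a low or zero complication count could partly reflect the filter, and nothing in the collected data would show it.

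**Working it through.** The plan gives no figure on this point to reproduce. The check is a trace through the text, followed by an illustration on assumed rates.

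**1. What can happen to a non-fatal serious event**

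| Site's judgement | Reported? | Can the CEC change it? |
|---|---|---|
| Device-related and MRI-related | Yes (8.3.2) | Yes, it can remove the MRI link |
| Device-related, not MRI-related | Yes (8.3.2) | Yes, it can add the MRI link (8.2.2) |
| Not device-related | No, outside the triggers below | No, it never arrives |

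**2. Routes that do not depend on a site judgement of device-relatedness**

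- Deaths: all are reported and classified (8.4.1, 14.1). No gap.
- Sustained ventricular arrhythmia, asystole or reproducible arrhythmia during the scan: an Adverse Event form is required with no causality condition (6.4.3). The text does not say whether that form goes to the CEC if the site calls the event unrelated.
- Pacing-threshold rise from before to after the scan: reported as an ADE or SADE on a measured change (6.5.2), so it falls within the CEC's remit.
- System revisions: generator replacement, lead replacement and lead repositioning go on a System Revision form whatever the cause (6.7). Routing to the CEC is not stated, and a pocket-only revision is exempt.

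**3. Routes that might seem to close the gap**

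- Potential UADEs: section 8.1.4 requires the effect not to have been identified beforehand in the plan. Thrombus, embolism, pulmonary embolism and VT/VF are in Table 1, so this route generally does not help with them.
- Unscheduled visits: defined as visits due to an ADE, SADE or UADE (6.6.4), so the same filter applies.
- The prompted work-up for clotting or embolism (6.5.2): covers symptoms during or just after the scan, not later ones.

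No section sends a non-fatal event to the CEC simply because it is serious.

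**4. Illustration (rates assumed, not from the documents)**

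Let n = 300 (section 4.2.1). Let r be the true rate of non-fatal MRI-related complications not caught by a trigger, and s the share of them the site labels device-related. Then the expected number seen is n·r·s, and P(none seen) = (1 − r·s)^300.

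| r | s = 1.0 | s = 0.8 | s = 0.5 |
|---|---|---|---|
| 0.5% | 1.5 seen; P(none) 22.2% | 1.2; 30.0% | 0.75; 47.2% |
| 1% | 3.0; 4.9% | 2.4; 9.0% | 1.5; 22.2% |
| 2% | 6.0; 0.2% | 4.8; 0.8% | 3.0; 4.9% |

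For example, at r = 1% and s = 0.5, (1 − 0.005)^300 = 0.222, against (1 − 0.01)^300 = 0.049 with full capture.

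The effect is small when recognition is high. With 2 expected events and s = 0.9, the Poisson probability of seeing none is exp(−1.8) = 16.5%, against exp(−2) = 13.5%.

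**5. Load of the fix (assumption)**

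If 3% to 10% of subjects have a serious adverse event in about a month, the extra forms number 300 × 0.03 = 9 to 300 × 0.10 = 30.

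**The case against.** Collecting only device-related events is a stated choice in a registry of clinically indicated scans whose primary endpoints concern image quality. There is no hypothesis (12.9) and no pass/fail criterion (12.3), so only a descriptive table is affected. Many serious events, such as a pulmonary embolism managed without an invasive procedure, would not meet the complication definition in 8.2.1 even if reported. Generator and lead revisions, which are invasive, already leave a record. On one reading of 8.2.2, a complication must also arise by the end of the MRI scan visit, which would shrink the relevant window. The event rates and recognition rates above are all assumed. All of this stands. It limits the importance of the gap but does not close it.

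Two stronger readings are tempting, and the documents do not support them.

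- A reader might infer that adjudication can only remove attributions, never add one. Section 8.3.2 makes device effects not linked to the scan reportable, and the CEC decides MRI-relatedness from more than the site's opinion: "The CEC will base their final adjudication on the information provided on the case report forms, medical records, and their clinical knowledge and experience". It can add an MRI link the site missed. What it cannot supply is missed device-relatedness.
- Section 14.2 says that "the Steering Committee will also monitor the overall safety through ongoing monitoring of adverse event and death rates", and a reader might infer that the Steering Committee is asked to follow rates nobody collects. But sections 4.4.2, 6.6.5 and 12.1.3 use the general term as shorthand for ADEs, SADEs and UADEs, which are collected.

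The case report forms and the CEC charter are held separately, so their detail cannot be checked here.

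**Conclusion.** The point holds in limited form. Outside deaths and the objective triggers, a non-fatal serious event that the site calls unrelated to the device is not reportable and is outside the CEC's remit. For those events the adjudicated MRI-related complication count can err only toward under-counting.

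The documents do not give the size. It depends on the true rate, on how often sites recognise relatedness, and on how the time window in 8.2.2 is read. Over the assumed ranges (r from 0.5% to 2%, s from 0.5 to 1.0), the increase in the chance of seeing none runs from nil to about 25 percentage points (47.2% − 22.2%). The primary endpoints are untouched. This is an inexpensive improvement to a descriptive safety count, not a defect in the main analysis.

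**What to change.** In sections 8.3, 8.3.2 and 14.1:

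- From MRI programming to the last scheduled follow-up, require every serious adverse event to be reported on the existing Adverse Event form, whatever the site's view of causality. The seriousness criteria in 8.1.3 can serve unchanged.
- Record the site's causality opinion as a field on that form, and have the CEC assign device-relatedness and MRI-relatedness.
- Route the System Revision forms already collected under 6.7 to the CEC.

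Leave non-serious event reporting, the NSVT and PVC exemption in 6.4.3 and the Table 2 exemptions as they are. Extending causality-free reporting to non-serious events of the Table 1 types would collide with those exemptions.

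The cost is protocol wording, a causality field, 9 to 30 extra forms over the study on the assumption in the working, and slightly more CEC work. The form, the committee and the visits already exist.
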